5 STUDY POPULATION

5.1 Inclusion Criteria

1. Adult ≥ 18 years of age
2. Laboratory-confirmed SARS-CoV-2 infection as determined by PCR or other authorized or approved assay in any specimen collected within 72 hours prior to enrollment.

Note – An exception must be requested to the Sponsor if ≥ 72 hours since positive test.

3. Hospitalized in participating facility.
4. Documentation of pneumonia with radiographic evidence of infiltrates by imaging (e.g., chest x-ray or CT scan).
5. Abnormal respiratory status that is judged worse than baseline by the investigator and as documented at any point within 24 hours prior to randomization, consistent with ordinal scale levels 5, 6 or 7, specifically defined as:
 - Room air saturation of oxygen (SaO_2) $< 93\%$, OR
 - Requiring supplemental oxygen, OR
 - Tachypnea with respiratory rate ≥ 30
6. Patient or proxy is willing and able to provide written informed consent and comply with all protocol requirements

5.2 Exclusion Criteria

1. Contraindication to transfusion (e.g., severe volume overload, history of severe allergic reaction to blood products), as judged by the investigator.
2. Clinical suspicion that the etiology of acute illness (acute decompensation) is primarily due to a condition other than COVID-19
3. Receipt of other investigational therapy as a part of another clinical trial.
 - a. *Note: investigational therapies used as part of clinical care, (eg, remdesivir, hydroxychloroquine) are permissible.*

5.3 Lifestyle Considerations

Not applicable.

5.4 Screen Failures

After the screening evaluations have been completed, the investigator or designee is to review the inclusion/exclusion criteria and determine the participant's eligibility for the study.

Only the reason(s) for ineligibility will be collected on screen failures. Participants who are found to be ineligible will be told the reason(s) for ineligibility.

Individuals who do not meet the criteria for participation in this study (screen failure) because of an abnormal laboratory finding may be rescreened once.

5.5 Strategies for Recruitment and Retention

5.5.1 *Recruitment*

Screening will begin with a brief discussion with study staff. If patient is mechanically ventilated and both studies are open to enrollment, information about both PennCCP-01 and PennCCP-02 will be provided to all potential participants and or legally authorized representative. Information regarding the risks and benefits and scientific aims of the single arm study PennCCP-01 and the randomized, controlled study PennCCP-02 will be presented. If patient is ineligible for PennCCP-01, information about this randomized study only will be presented to potential participants (or legally authorized representative) and questions will be asked to determine potential eligibility. Screening procedures can begin only after informed consent is obtained by a Study Investigator.

5.5.2 *Retention*

Retention of participants in this trial is very important for determining the primary endpoint. As such, after hospital discharge, participants will be reminded of subsequent study visits and every effort will be made to accommodate the participant's schedule to facilitate follow-up within the specified visit window. Additionally, there are many circumstances that influence the ability to obtain outcome information after discharge. Follow-up visits may be conducted by phone if in-person visits are not feasible. Data and samples may be collected from subject's home, office, or hospital visits.

5.5.3 *Costs*

There is no cost to participants for the research tests, procedures/evaluations and study product while taking part in this trial. Procedures and treatment for clinical care including costs associated with hospital stay may be billed to the participant, participant's insurance or third party.

6 STUDY INTERVENTION

6.1 Study Intervention(s) Administration

6.1.1 *Study Intervention Description*

Participants in the treatment arm will receive standard care plus 2 units of COVID-19 convalescent plasma on Study Day 1. Participants will receive plasma compatible with their blood type (per standard blood bank practice).

6.1.2 *Dosing and Administration*

Participants will be randomized 1:1, stratified on mechanical ventilation and receipt of remdesivir at baseline, to receive either PCCP and standard care (treatment arm) or standard care alone (control arm).

For those participants assigned to the treatment group, the study plasma should be administered as soon as possible. Before administration of study plasma, the investigator must check for appropriate investigational study label on the plasma bag.

The calendar date and 24-hour clock time for study plasma administration should be recorded for the start and end of each infusion. The two infusions should be separated by at least 1 hour after the end of the first and the start of the second infusion in order to assess for any immediate AEs from the first unit. The interval may be extended if clinically indicated. This should be noted on the infusion record and will not be considered a protocol violation.

If an AE considered related to the administration of the investigational product occurs during infusion, the infusion may be slowed temporarily or permanently discontinued, as deemed appropriate by the investigator. As a guide, local side effects (e.g., infusion site burning), nonallergic systemic effects (e.g., chills), and mild allergic reactions (itching, hives) can generally be alleviated by slowing the rate of infusion, whereas serious allergic side effects (e.g., wheezing, hypotension) should result in the cessation of study plasma infusion. The treating investigator is ultimately responsible for making the decision to slow or stop study plasma infusion. If the infusion is discontinued, the participant should be treated according to best available local practices and procedures, and the Principal Investigator should notify the Sponsor Medical Director and HUP Blood Bank. Reason(s) for premature discontinuation of any plasma infusion must be documented in the medical record (source document) and on the CRF.

As with any foreign protein, allergic reactions to dose administration are possible. Therefore, appropriate drugs such as Benadryl® and epinephrine and medical equipment to treat acute allergic reactions must be immediately available, and study personnel must be trained to recognize and treat allergic reactions. If generalized urticaria, hypotension, or anaphylaxis occurs, the infusion of plasma should be immediately discontinued. Treatment should be given in an appropriate timeframe as medically indicated.

All participants will be observed for at least 1 hour after administration of study plasma. Appropriate medical treatment should be given as needed based on best available local practices and procedures.

6.2 Preparation/Handling/Storage/Accountability

6.2.1 Acquisition and Accountability

The Penn Blood Bank will release a thawed product, in a bag containing between 200-250 mL. The Principal Investigator will ensure an adequate accountability of the investigational product

6.2.2 Formulation, Appearance, Packaging, and Labeling

The product ready to be administered will be provided in a bag labelled using an ISBT-128 compliant label and will include the investigational product language as required by regulation. Product Storage and Stability.

Product will be stored in the HUP Stem Cell Laboratory until it is released to the PI at the time of transfusion.

6.2.3 Preparation

Preparation: Frozen product will be transported from the HUP Stem Cell Laboratory back to the HUP Blood Bank to be thawed before issuing to the patient's transfusion team.

6.3 Measures to Minimize Bias: Randomization and Blinding

Individuals will be randomized to the intervention or control arm in a 1:1 ratio. Randomization will occur in a blinded fashion using Redcap. Allocation will be determined using a permuted block algorithm with varying block sizes. We will stratify randomization based on whether or not a patient is on mechanical ventilation and on [remdesivir](#) at baseline. Though the intervention will not be blinded, we will attempt to minimize bias by blinding study personnel, such as individuals running laboratory assays, to the extent that it is possible.

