The alternative to participation in this study is routine standard of care, which can include supplemental oxygen, fluids, and other symptomatic treatments. Additional treatments for this type of participants may include experimental antivirals and/or immunomodulators (e.g., hydroxychloroquine) determined by clinical practice and the rapidly evolving evidence base.

2.3.3 **Assessment of Potential Risks and Benefits**

There is a substantial risk of morbidity and mortality in COVID-19 disease, especially in intubated, mechanically ventilated patients. Mortality rates vary across clinical cohorts, but recent reports suggest mortality rates up to 28% in hospitalized patients in China (REFS). At this time, there are no effective COVID-19 therapeutics and standard of care involves supportive therapy (e.g., oxygen, fluids), with consideration of a variety of unproven, experimental treatments (e.g., antivirals and immunomodulators).

The administration of blood products, including plasma, is a common and well tolerated clinical option used in multiple indications. There are limited reports of the effects of convalescent plasma for COVID-19, with just two small observational studies describing a total of 15 patients, to date [30, 31]. The experience from these studies and studies of convalescent plasma in other viral infections suggest that plasma administration is safe and well tolerated and may confer clinical benefit. Thus, for severe COVID-19 disease, the possible therapeutic benefit of convalescent plasma outweighs the minimal safety risks.

2.3.3.1 *Assessment of Potential Risks and Benefits in Pregnant Individuals*

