4 STUDY PLAN

4.1 Study Design

80 participants will be enrolled and randomized. All participants will be followed through Study Day 60. The study population will consist of adults >18 years of age hospitalized, intubated and mechanically ventilated with confirmed COVID-19 pneumonia caused by SARS-CoV-2.

This randomized, controlled, open-label, phase 1 trial will assess the safety and efficacy of convalescent plasma in severely ill, hospitalized participants with pneumonia due to COVID-19. This study will enroll adults over the age of 18, including pregnant women.

A total of 80 eligible participants will be randomized 1:1 to either receive standard care and 2 units of convalescent plasma collected from ABO-compatible donors who have recovered from COVID-19 or standard care alone. Participants in the treatment arm will receive convalescent plasma on Study Day 1 in addition to standard care. Participants will be assessed daily while hospitalized through Study Day 29. Participants discharged from the hospital will be asked to attend remaining study visits at Study Days 15, 22, 29, and 60. The Study Day 22 visit may be conducted by phone. All participants will undergo a series of safety, efficacy, and laboratory assessments. Blood samples will be collected on Days 1 (prior to plasma administration), 3, 5, 8, 11, 15, 29, and 60. Oropharyngeal or endotracheal samples will be collected as possible on Days 1 (prior to plasma administration), 3, 5, 8, 11, and 15. Given the COVID-19 restrictions and the difficulty some of the participants might have to attend an in person visit after hospital discharge, the collection of Day 60 data for primary and secondary endpoints and the collection of Day 60 research samples for exploratory tests may be performed up to 90 days following the Day 60 visit.

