- The key parameter of interest will be the comparison of clinical severity between individuals receiving the experimental intervention versus control, as measured by a clinical severity score that takes into account the modified 8-point ordinal severity score in a prioritized manner. For the modification, recovery will be defined by reaching levels 1-3 on the 8-point ordinal severity score. The null hypothesis is that experimental individuals will have the same median severity as control individuals. The severity score is based on a procedure by Shaw and Fay 2016 [21], which ranks participants based on their Day 29 ordinal severity. All survivors better than non-survivors, individuals with shorter recovery times as better, and individuals with shorter times to death as worse. For individuals who survive but had not yet recovered by Day 29, they will be ranked according to their Day 29 ordinal severity, with individuals achieving the same ordinal severity being ranked according to time to reaching that level of severity. More details are provided in the Statistical Analysis Plan (SAP). This type of severity score, or prioritized outcome, has been advocated in many settings such as infectious disease and cardiovascular outcome settings [22,24,25]. This analysis will have more power to detect differences than looking only at one individual endpoint. Shaw and Fay 2016 showed this test statistic can be interpreted as a weighted average of the log-rank type test statistic for survival and the one for time to recovery amongst survivors. The individual endpoints, time to recovery and time to death, will also be examined as secondary endpoints.
- **Secondary Efficacy Endpoint(s):** Comparison between arms of time to recovery and survival.
- The null hypothesis is that the two arms will have the same recovery time and the same survival time. Kaplan-Meier survival curves will be calculated by arm and compared with a Peto-Peto generalized Wilcoxon test. In the event that deaths occur, the cumulative incidence of recovery will be estimated and compared between groups using Gray's test, which will be able to capture a lower time to recovery due to either a slower event rate or a higher death rate. For interpretive purposes the cause specific hazard ratios for will also be calculated for each event type,

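### Randomisation is stratified by ventilation and remdesivir, but Section 9 tests the primary and key secondary endpoints by arm only: valid, but less powerful if ventilation is strongly prognostic

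*Combined protocol and SAP*

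**What the plan says.** **Design.** Section 6.1.2 has participants randomised 1:1, "stratified on mechanical ventilation and receipt of remdesivir at baseline". Section 6.3 repeats this ("We will stratify randomization based on whether or not a patient is on mechanical ventilation", plus remdesivir) and specifies permuted blocks of varying size. The amendment history (10.3) gives the purpose of the remdesivir stratum as allowing analysis by remdesivir use.

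**Analysis.** Sections 9.1, 9.2 and 9.4.2 define the primary efficacy comparison as a prioritised ranking: deaths last (earlier is worse), unrecovered survivors by Day 29 level and time to reach it, recovered patients by time to recovery. It is compared between arms with no stratum or covariate. For the key secondary endpoints, "Kaplan-Meier survival curves will be calculated by arm and compared with a Peto-Peto generalized Wilcoxon test" (9.1, repeated in 9.4.3), with Gray's test for recovery if deaths occur. Again no stratum is named. Section 9.4.7 lists age, sex and symptom duration as subgroups. Sections 9.1 and 9.4.1 to 9.4.3 leave further detail to an SAP, which 9.4.1 says will be written before the endpoints are analysed.

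**Population.** Section 5.1 admits respiratory status "consistent with ordinal scale levels 5, 6 or 7", so both ventilated and non-ventilated patients can enter. Section 4.1 describes participants as "hospitalized, intubated and mechanically ventilated with confirmed COVID-19 pneumonia".

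**The concern.** Stratified blocks balance the arms on ventilation. A test that ignores the strata still counts the difference between ventilated and non-ventilated patients as random noise. It therefore overstates the variance of its own statistic: it rejects too rarely under the null and misses some real effects.

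That ventilation is prognostic is plausible from the protocol. Section 2.3.3 says: "There is a substantial risk of morbidity and mortality in COVID-19 disease, especially in intubated, mechanically ventilated patients". Entry also spans three levels of the scale that forms part of the outcome. The protocol does not quantify the difference.

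At stake is power for effects smaller than the planned one, in a trial whose Section 9.2 wants a preliminary reading of efficacy. The trial is open-label, so a choice between stratified and unstratified tests made late could be criticised as data-driven.

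**Working it through.** **1. The plan's own power figures (9.2) reproduce.**
- Primary: binomial, n = 40 pairs, null 0.50, two-sided 0.05. The critical value is 27, since P(X ≥ 27 | 0.50) = 0.019. Power is P(X ≥ 27 | 0.80) = 98.1%, consistent with over 80%.
- Secondary, 0.50 vs 0.80 with 40 per arm: z = (0.30·√40 − 1.96·√(2·0.65·0.35)) / √(0.25 + 0.16) = (1.897 − 1.322)/0.640 = 0.90, so power is 81.6%, consistent with about 80%.

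None of these figures is disputed.

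**2. The two tests.**
- Unstratified: Z = (W − n₁(N+1)/2)/√V, with V = n₁n₀/(N(N−1))·Σ(rᵢ − r̄)². The sum includes the between-stratum spread, although stratified blocks largely remove that spread from W.
- Stratified (van Elteren): Z = Σₛ[(Wₛ − n₁ₛ(nₛ+1)/2)/(nₛ+1)] / √Σₛ[Vₛ/(nₛ+1)²], which uses ranks within strata only.

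**3. Simulation of the prioritised ranking.** From the documents: 80 patients, 1:1, stratified blocks, two-sided 0.05. Assumed: constant daily hazards to Day 29; 50% on remdesivir, not prognostic; block sizes 2, 4 and 6. Each power cell has 4,000 trials (Monte Carlo SE at most 0.5/√4000 = 0.8 points).

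Assumed Day 29 death/recovery in controls, non-ventilated then ventilated:
- strong: 8/85% and 45/25%
- moderate: 12/75% and 35/40%
- weak: 17/70% and 23/60%
- none: 20/65% in both

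For the strong and moderate cases with 10–50% ventilated, control mortality runs from 0.9·8 + 0.1·45 = 11.7% to 0.5·8 + 0.5·45 = 26.5%. Section 2.3.3 says "recent reports suggest mortality rates up to 28% in hospitalized patients in China".

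Assumed treatment effects:
- A: death HR 0.65, recovery HR 1.5 (within-stratum win probability 0.60)
- B: 0.5 and 1.9 (0.65)
- C: 0.3 and 4.5 (0.81)

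Primary-test power (%), unstratified / four strata / ventilation only:

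| Prognosis, share ventilated | A | B |
|---|---|---|
| Strong, 50% | 17.3 / 31.1 / 32.2 | 45.8 / 64.4 / 65.6 |
| Strong, 30% | 20.8 / 31.6 / 32.3 | 49.8 / 64.9 / 65.6 |
| Strong, 10% | 26.8 / 31.8 / 32.4 | 61.3 / 65.9 / 66.6 |
| Moderate, 50% | 28.3 / 32.4 / 33.0 | 60.3 / 65.2 / 66.5 |
| Moderate, 30% | 28.5 / 31.5 / 32.7 | 61.3 / 65.1 / 66.2 |
| Moderate, 10% | 31.7 / 33.2 / 33.5 | 65.3 / 66.2 / 66.9 |
| Weak, 30% | 33.4 / 32.9 / 33.3 | 67.0 / 66.2 / 67.2 |
| None | 32.9 / 32.2 / 32.4 | 69.0 / 67.0 / 68.3 |

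Under C with strong prognosis, every version has 99.7–100%. If all patients were ventilated, as Section 4.1 reads, stratifying by remdesivir alone gives 30.9 to 30.5 (A) and 63.2 to 62.1 (B).

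**4. Key secondary tests**, unstratified / stratified by ventilation (%). The log-rank test stands in for Gray's test, with deaths counted as never recovering; survival uses Peto-Peto.

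| Prognosis, share ventilated | Recovery A | Recovery B | Survival A | Survival B |
|---|---|---|---|---|
| Strong, 50% | 14.4 / 32.4 | 41.2 / 67.7 | 16.3 / 20.1 | 35.4 / 39.6 |
| Strong, 30% | 19.0 / 36.9 | 45.7 / 71.2 | 13.0 / 16.8 | 25.0 / 29.6 |
| Moderate, 50% | 30.2 / 36.2 | 65.8 / 72.4 | +1.2 to +1.9 points | +1.2 to +1.9 points |
| Moderate, 30% | 31.2 / 37.1 | 67.3 / 73.7 | +1.2 to +1.9 points | +1.2 to +1.9 points |

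With weak or no prognosis the change is −0.9 to +0.3 points.

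**5. Null rejection of the primary test** (20,000 trials), unstratified / four strata / ventilation only: strong 50%, 1.8 / 5.0 / 4.9%; strong 30%, 2.5 / 5.1 / 5.0%; moderate 50%, 4.0 / 5.4 / 5.4%. With weak prognosis at 30% ventilated, a run of 6,000 trials gave 5.0% unstratified, so the conservatism disappears there.

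**6. Check with a different model.** Logistic latent severity, treatment odds ratio 3.3, remdesivir odds ratio 1.5, 20% or 50% ventilated. Power, unstratified vs four strata:
- ventilation odds ratio 1: 84.6 vs 83.5 (20% ventilated), 85.0 vs 84.1 (50%)
- odds ratio 3: 83.7 vs 84.8, 82.3 vs 84.5
- odds ratio 10: 76.3 vs 84.3, 70.3 vs 84.1
- odds ratio 30: 68.5 vs 83.5, 53.6 vs 83.6

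Unstratified null rejection was 0.5–4.8%, never above 5%.

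**The case against.** The case for leaving this alone has real parts:

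- **Deferral.** The plan hands detail to an SAP that is not supplied, and the amendment history shows an intention to use at least the remdesivir stratum. Nothing shows that the strata will be ignored. This stands, and it limits the point to what Section 9 says. The only remdesivir analysis there is the comparison with recipients in another protocol (9.4.9).
- **No stated figure fails.** Type I error is not inflated, power near the planned effect is close to 100% either way, and the sample size is driven by safety. This stands, and makes it an efficiency point. Under effect A, power is low even after stratifying (about 31–33%).
- **The size is assumed.** The 11–20 point gain needs a sharp contrast: a non-ventilated patient does better with probability 0.83, roughly an odds ratio of 10. The ventilated share may also be low. Section 5.5.1 says "If patient is mechanically ventilated and both studies are open to enrollment", information on the single-arm study is given as well, which could draw ventilated patients away. At 10% ventilated the gain is 1–6 points. This stands; only the direction follows from the design.
- **The ordering of the secondary endpoints** (recovery gains most, survival least) reflects the assumed hazards and is not a general result.
- **The target changes**, from a marginal to a within-stratum win probability. This is true and should be stated in the SAP.

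None of this removes the asymmetry: up to about 2 points lost on the primary test if the strata do not matter, against as much as 20 gained if they matter strongly.

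**Conclusion.** The concern holds. Section 9 does not carry the randomisation strata into the primary or key secondary tests, and 9.4.7 lists neither factor. The planned tests are valid. They are conservative only if ventilation is at least moderately prognostic: null rejection of the primary test was 1.8–4.0% in the three strong or moderate settings run at 30–50% ventilated.

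The gain from stratifying, for within-stratum win probabilities of 0.60–0.65:

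- Primary test, 30–50% ventilated: 3–6 points (moderate) or 11–20 (strong).
- Primary test, 10% ventilated: 1–6 points.
- Primary test, weak or no prognosis: −2.0 to +0.2 points in the cells shown.
- Time to recovery, 30–50% ventilated: about 6–7 points (moderate) or 18–27 (strong).
- Survival, 30–50% ventilated: 1–2 points (moderate) or 4–5 (strong).

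Confidence is high for the silence of Section 9 and the direction of the effect. The size depends on the assumed ventilated share, prognosis and treatment effect. The plan should change, but its conclusions would not be invalid without the change.

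**What to change.** In 9.4.2 and the SAP, before any endpoint analysis:

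1. Compare the same severity ranking within randomisation strata, by a van Elteren-type or stratified permutation test. Keep the unstratified test as a sensitivity analysis.
2. Fix in advance a rule for pooling to ventilation alone, based on cell counts and without outcomes by arm. At 10% ventilated, about 8 of 80 patients would be spread over two remdesivir cells.
3. Stratify the survival and time-to-recovery tests by ventilation. The other secondary tests can stay as planned.
4. State that the target is a within-stratum win probability.
5. Optionally, add ventilation and remdesivir to the descriptive forest plot in 9.4.7.

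Separately, reconcile Sections 4.1 and 5.1 on whether non-ventilated patients are in the study population. If all are ventilated, that stratum has no contrast.

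The cost is SAP wording and a few lines of code, since the strata are recorded at randomisation. If they prove not prognostic, the primary test loses up to about 2 points, or under 1 if pooled to ventilation. The asymptotic stratified recovery test rejected 5.4–5.5% under the null (Monte Carlo SE 0.16 points); a permutation reference avoids this.
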